Specific Aims: We will conduct an Evidence Based CRC Prevention Program, among uninsured 50-64 year olds served by the JPS safety-net health system, not up-to-date with screening, with the following aims:

Aim 1: Deliver mailed invitations to complete FIT screening to all eligible patients (over 20,000), with centralized processes to promote screening completion and evidence based follow up, including repeat annual FIT for patients with initial normal FIT.

Aim 2: For a randomly assigned subset of 2,000 patients, supplement the mailed outreach invitations with modest financial incentives to complete screening with either a \$5 or \$10 gift card.

Aim 3: Rigorously evaluate program outcomes. We will:

- A) Determine screening rate improvement after expanding screening outreach to all unscreened patients.
- **B)** Compare rates of initial and repeat screening completion among 1) Patients offered a modest financial incentive to complete screening, in addition to outreach invitations, vs. 2) Patients offered outreach invitations alone.

- **C)** Among patients receiving financial incentives to complete screening, compare rates of initial and repeat screening completion between patients receiving \$5 vs. \$10 incentives.
- **D)** Assess all CPRIT required outcomes, including increase in early stage cancer detection from baseline, as well as health system changes required to boost screening.

By completing these goals, we expect to reach over 20,000 patients with screening invitations, screen over 6,600 patients, and detect 400 patients with CRC or potentially precancerous polyps.

Innovation: We will translate findings from our prior CPRIT program to usual practice by developing knowledge and infrastructure required at JPS for successful, sustainable screening outreach. Also, we will determine if offering modest financial incentives enhances mailed outreach, further advancing prevention knowledge.

Significance and Impact: Locally, we will deliver potentially lifesaving screening invitations to over 20,000 patients, and create a robust, sustainable CRC screening program poised to markedly improve CRC outcomes for uninsured patients in Tarrant County, TX. Statewide and nationally, our program will advance cancer prevention knowledge, and serve as a proven, replicable model for improving CRC screening for the uninsured.

Background:

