As a result of the new program, we will create a sustainable CRC screening outreach program for uninsured patients in Tarrant County and Fort Worth, Texas. The program will serve as a model for other health systems which care for uninsured patients across Texas and beyond. Also, we may discover new ways to convince more patients to be screened that can be used locally and nationally. Most importantly, we will offer potentially lifesaving CRC screening to over 20,000 patients, expect over 6,600 patients will get screened, and predict we will find 38 patients with CRC and 364 patients with potentially precancerous polyps.

Study Procedures:

Overview: Our program is set at John Peter Smith Health System (JPS), a safety-net health system serving Tarrant County, TX. Our prevention program will systematically identify uninsured, 50 to 64 year old patients, not up-to-date with screening, and deliver over 20,000 organized invitations to complete screening with a FIT. Organized outreach will consist of a mailed invitation to complete screening, information regarding importance of CRC screening, and a FIT kit. Screening participation will be promoted with automated phone reminders before and after invitation delivery, as well "live" phone reminders. Guideline appropriate follow up will be delivered, including facilitation of colonoscopy for patients with abnormal FITs, and annual repeat FIT invitation for patients with normal FITs. To understand impact of offering financial incentives on screening completion, for a subset of randomly assigned patients, screening promotion will be supplemented with an additional modest \$5 or \$10 gift card incentive for completing screening.

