Centralized processes to promote guideline-based follow up. Follow up for patients with a normal test in Year 1 will consist of repeat screening invitations in Year 2 and Year 3. This is consistent with guideline recommended annual FIT for CRC screening^{13, 14}. Follow up for patients with an abnormal FIT will consist of navigation to complete a colonoscopy. Up to 10% of individuals with an abnormal FIT have a colon cancer, and up to 50% may have a potentially precancerous polyp^{44, 45}. Thus, colonoscopy follow up is imperative. Patients with abnormal FIT will be called by the screening team within 1 week to report the result and facilitate direct scheduling of colonoscopy or a pre-colonoscopy visit. During their pre-colonoscopy visit patients will receive a Gatorade Bowel Prep kit with instructions on how to prepare for their colonoscopy. If colonoscopy scheduling is delayed, there is a possibility that the Dulcolax tablets in prep kits may expire. Expiration dates will be monitored by the study team. In the event tablets will reach expiration before a scheduled colonoscopy, the patient will be mailed a letter with replacement tablets. The goal will be to schedule colonoscopies within 12 weeks of the abnormal FIT. In our prior outreach program, all patients willing to have their colonoscopies done within 12 weeks were accommodated, most within a much shorter period of time. Patients who do not keep their scheduled pre-colonoscopy or post-colonoscopy appointment will be contacted by phone to reschedule their missed visit. Patients who the study team are unable to contact by phone will be mailed a "No-Show" letter asking them to call the JPS clinic to reschedule their appointment. Similarly, patients who do not keep their scheduled colonoscopy will be contacted by phone to reschedule their colonoscopy. Those patients that the team is unable to contact by phone will be mailed a "No-Show" letter asking them to contact the JPS clinic to reschedule their colonoscopy. After multiple attempts to reach No-Show patients by phone and certified letter, a final letter will be mailed to them. The letter informs patients that this is the final attempt to remind them that they had an abnormal FIT and to contact the JPS staff to schedule an appointment for further evaluation, possibly with colonoscopy. All three letters will be on JPS letterhead signed by [name] and include a contact phone number for the study team.

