 HEDIS criteria were selected because these are standardized criteria that the National Committee on Quality Assurance uses to compare rates of CRC screening across different insurance carriers. The criteria are clear, and widely available, and using these criteria will improve generalizability of our program procedures. In prior published analyses, we previously demonstrated ability to determine screening rates and identify patients not up to data using a similar approach, and validated the approach for this purpose^{19, 42}. Table 3 shows codes that will be used to assess whether patients are screening up-to-date.

Criteria for Exclusion of Subjects:

Patients with a history of CRC or colon resection, no address and/or phone number on file, or who are incarcerated will be excluded. Patients with history of CRC/colon resection will be excluded because they require specialized screening, usually with colonoscopy. Addresses and phone numbers are required to deliver outreach. Incarcerated patients will be excluded because they cannot keep FIT kits in their cells.

Once included, patients will remain in the program unless they no longer meet age criteria. Patients in both the standard (non-incentive) and incentive invitation groups who do not respond to initial invitation will be followed for screening outcomes, but will not receive repeat

Version 8, June 29, 2015

invitations. Through the program period, we expect that some patients will no longer participate in the JPS connection program, or not see a primary care provider within a year. We considered excluding these patients in subsequent years, but decided against this. Many of these patients remain uninsured, and if they were to develop late stage CRC, would present to JPS for treatment. We anticipate that most of these patients would then again access the JPS medical assistance program for the uninsured as well as primary care clinics, because JPS is the main safety-net health system for uninsured patients in Tarrant County and Fort Worth, TX. Continuing screening outreach will potentially allow for boosting detection of such patients when their CRCs are early, rather than late stage.

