Additional patients will be assessed for inclusion/exclusion criteria annually in Years 2 and 3 of the program. Each year, patients who newly meet our inclusion/exclusion criteria will be included in the program. For example, patients newly turning 50 in year 2 or 3 meeting all other inclusion/exclusion criteria will receive screening outreach. Similarly, a 60 year old patient new to the JPS system and meeting inclusion/exclusion criteria will also receive screening outreach. We think this approach reflects the ideal implementation of a standing CRC outreach program.

Sources of Research Material:

There are several sources of research material for this project:

- Administrative and electronic medical record databases at JPS. These data systems will be used to identify patients meeting inclusion/exclusion criteria, and to record outcomes of screening invitation.
- **Results of fecal immunochemical tests (FIT).** Patients will be invited to complete screening with a one-sample FIT. These kits will be processed by the JPS clinical lab, and the results will be recorded in the electronic medical record. Results of testing, including whether the test was abnormal or normal, and the level of hemoglobin present in the sample, will be collected
- **JPS cancer registry**. This resource will be accessed to identify patients enrolled in the screening program who develop CRC during the follow up time frame.
- **Study tracking database**. This database will record in real-time delivery of all screening interventions, and outcomes of the interventions. In addition, process variables, such as time spent on phone with patients, failed mailings due to wrong address will be collected. The study tracking database has been created for exclusive use by screening program personnel.
- Interviews of JPS personnel who will be conducting outreach interventions. The purpose of these interviews will be to understand the challenges to implementation of the outreach program within the health system.

Variable	Justification	Source
Baseline characteristics and elig	gibility criteria	
first name, last name	Required for delivery of	JPS administrative and
	screening invitations	electronic medical record
date of birth	Required for eligibility criteria	databases
Sex	Screening rates can differ by	
	sex	
Race/ethnicity	Screening rates may differ by	
	race/ethnicity	
Primary language	Use to identify preferred	
	language for study interventions	
Home address	Required for screening	

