we will even have 90% power to detect a smaller screening rate increase of \geq 5% (Power was computed with nQuery Advisor Software v.7.0).

Evaluation Aim B) Compare rates of initial and repeat screening completion among 1) Patients offered a modest financial incentive to complete screening, in addition to outreach invitations (n=2,000), vs. 2) Patients offered outreach invitations alone (n=~18,000). The rate of initial screening completion will be defined by:

Initial	# patients completing a FIT
Screening	Year 1
Completion Rate =	# of patients sent FIT invitation Year 1

We will compare the initial screening completion rate for patients offered the financial incentive, in addition to screening outreach, to the initial rate for patients offered screening outreach alone using a Chi-square test of proportions, with a 2-sided p value <0.05

considered statistically significant. The rate of repeat screening for Years 2 and 3 will be defined by:

Year 2	# patients completing FIT	Year 3 Repeat	# patients completing FIT
Repeat	screening Year 2	Completion	screening Year 3
Completion	# patients completing FIT Year 1	Rate =	# patients completing FIT Year 2
Rate =	with normal result		with normal result

We will compare initial FIT completion rates for the financial incentive plus organized outreach vs. organized outreach alone groups using a Chi-square test, with a 2-sided p value <0.05 considered statistically significant. The same approach will be taken for comparing repeat FIT completion rates for Years 2 and 3.

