Sample size for Evaluation Aim B. The sample size for this aim will be 2,000 for the financial incentive group plus outreach group, and at least 18,000 for the outreach group alone. The sample size for the financial incentive group was chosen based on sample size required for sufficient power to detect expected differences between offers of \$5 and \$10 gift card incentives outlined in Aim C below. The sample size for the outreach group alone was based on including all patients included in the screening outreach program who will not receive financial incentives. With 2,000 patients assigned to the financial incentive plus outreach group, and 18,000 patients assigned to the outreach alone group, we estimate over 90% power to detect differences in initial screening participation of 5% or more at a 5% two-sided significance level. Thus, we will have more than enough power to detect clinically meaningful differences of 10% or more in initial FIT completion. Because of the lack of prior data on repeat FIT participation rates, and under the sample size discussion for Evaluation Aim A above, we do not present formal power calculations for comparisons of repeat FIT completion rates, but expect that we will be able to make meaningful comparisons based on the large number of patients included for evaluation.

Evaluation Aim C) Compare rates of initial and repeat screening among patients receiving \$5 vs. \$10 financial incentives in addition to outreach invitations. For this comparison, we will use the same definitions outlined under "Evaluation Aim B" above for the initial screening completion rate, and the Year 2 and 3 repeat completion rates. For these outcomes, we will compare the outcome rate for patients receiving the \$5 vs. \$10 incentive, using a Chi-square test of proportions, with a 2-sided p value <0.05 considered statistically significant.

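### The Year 3 repeat completion rate takes only Year 2 completers as its denominator, although the plan also re-invites patients who skipped Year 2

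*Combined protocol and SAP*

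**What the plan says.** **The formulas.** In the Biostatistics section, Evaluation Aim B, "The rate of repeat screening for Years 2 and 3 will be defined by" two ratios. Year 2 is FIT completers in Year 2 over Year 1 completers with a normal result. Year 3 is FIT completers in Year 3 over Year 2 completers with a normal result. Neither numerator is limited to members of its denominator. Both rates are compared between arms by a chi-square test at two-sided 0.05. Aim C carries the same ratios over to the comparison of the two gift-card amounts: "we will use the same definitions outlined under 'Evaluation Aim B' above for the initial screening completion rate, and the Year 2 and 3 repeat".

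**The invitation rule.** Four places bear on it:

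- Study Procedures, centralized follow-up: "Follow up for patients with a normal test in Year 1 will consist of repeat screening invitations in Year 2 and Year 3".
- Specific Aims, Aim 1: "repeat annual FIT for patients with initial normal FIT".
- Criteria for Exclusion, on who is not re-invited: patients "who do not respond to initial invitation will be followed for screening outcomes, but will not receive repeat" invitations.
- The same section, on retention: "Once included, patients will remain in the program unless they no longer meet age criteria".

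None of these makes the Year 3 invitation depend on completing Year 2. The Study Procedures overview is looser: "annual repeat FIT invitation for patients with normal FITs".

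**Later entrants.** The exclusion section adds: "Each year, patients who newly meet our inclusion/exclusion criteria will be included in the program". The Sub-Study Procedures say that all incentive patients were enrolled in Year 1 and that everyone new after that received the non-incentive invitation.

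**The concern.** A patient with a normal Year 1 FIT who skips Year 2 and returns the Year 3 kit has been invited and screened, yet the plan does not say how that FIT is counted. Read literally, it enters the numerator but not the denominator, so the ratio is not a proportion and a chi-square test of proportions is not defined for it. Read as nested, it is in neither part of the Year 3 repeat rate.

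The literal numerators have a second gap. If Year means program year, they also count first FITs from patients who joined after Year 1. Those patients are all in the outreach-alone arm, so the Aim B comparison would be affected on one side only.

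At stake is a question that the Introduction and Background put among the program's main ones: whether completion stays high when FIT is offered annually. Repeat completion is named in Aims B and C, both listed as primary evaluation aims.

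**Working it through.** The plan states no Year 3 repeat rate, so there is none to reproduce. Its yield estimate confirms two of the inputs: 20,000 × 0.33 × 0.12 = 792 abnormal FITs; × 0.048 = 38 cancers and × 0.46 = 364 adenomas, as printed under Secondary analyses.

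**Inputs from the plan.** Initial completion 33%; abnormal FIT 12%; repeat participation 40% to 75% (Aim A).

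**Assumptions.** The 12% also applies in Year 2. Patients with an abnormal Year 2 FIT are not counted as Year 3 invitees. Aging out is ignored. The skippers' Year 3 return rate *s* is not in the documents and is varied.

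**Step 1: who is outside the Year 3 denominator.** Let r2 be the Year 2 repeat rate. Per Year 1 normal patient, the denominator is 0.88 × r2 and the skippers are 1 − r2. The share of Year 3 invitees outside is (1 − r2) / (0.88 × r2 + 1 − r2).

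- r2 = 40%: 0.60 / (0.352 + 0.60) = 63%.
- r2 = 75%: 0.25 / (0.66 + 0.25) = 27.5%.

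The initial completion rate cancels, and no assumption about *s* is needed. In counts, 20,000 Year 1 invitations give 20,000 × 0.33 × 0.88 = 5,808 Year 1 normals. The denominator is then 2,044 with 3,485 skippers outside (r2 = 40%), or 3,833 with 1,452 outside (r2 = 75%).

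**Step 2: the three possible readings.** Let r3 be the Year 3 return rate among Year 2 completers with a normal result.

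- Literal: r3 + s × (1 − r2) / (0.88 × r2).
- Nested: r3.
- Among invitees: (0.88 × r2 × r3 + s × (1 − r2)) / (0.88 × r2 + 1 − r2).

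| r2 = r3 | s (assumed) | Literal | Nested | Among invitees |
|---|---|---|---|---|
| 40% | 10% | 57% | 40% | 21% |
| 40% | 20% | 74% | 40% | 27% |
| 40% | 40% | 108% | 40% | 40% |
| 75% | 37.5% | 89% | 75% | 65% |
| 75% | 75% | 103% | 75% | 75% |

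From skippers alone, the literal ratio passes 100% only when s exceeds 0.88 × r2: 35.2% at a 40% repeat rate, 66% at 75%.

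**Step 3: first-time completers, if Year means program year.** The sub-study describes 2,124 first-time invitees late in Year 2 and a 36% return rate: 2,124 × 0.36 = 765 FITs. As an illustration, assume that all 765 return within Year 2 and that the other 18,000 − 2,124 = 15,876 outreach-alone patients were invited in Year 1. The Year 2 denominator in that arm is 15,876 × 0.33 × 0.88 = 4,610, and 765 / 4,610 adds about 17 points (about 15 if initial completion is 36%). The incentive arm gains nothing from this source. Kits returned after the end of Year 2 would move part of this into Year 3.

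**The case against.** The strongest reply is that the measure is called a repeat rate and is tested as a proportion, so the nested reading is the natural one and only a limiting phrase is missing. That reading also fits the plan's benchmarks: the two repeat figures in the Background (75% and 44%) are both conditional on having completed an initial test. This stands. The nested rate is a legitimate consecutive-year adherence measure. But the plan does not say that this is what it intends, and it leaves unreported a group that the plan itself invites.

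The overview's looser wording could make the Year 3 invitation depend on the latest test. The more specific statements in Aim 1, the follow-up section and the exclusion section tie it to the initial test, and only non-response to the initial invitation ends it.

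On new entrants, Year may mean each patient's own year. The Aim B figure of about 18,000 outreach-alone patients fits that reading, and the problem then disappears. Elsewhere, however, the protocol uses Years 1, 2 and 3 for the program, and the formulas do not say which is meant. The skipper mismatch remains either way.

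Three stronger readings are tempting and not supported:

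- A reader might infer that the reported rate will exceed 100%. That needs skippers to return almost as often as consistent repeaters, or other completers to be counted.
- A reader might infer that returning skippers vanish from every Year 3 result. Aim A's end-of-Year-3 rate counts any eligible patient with a stool test in the last year, so they still count there.
- A reader might infer a biased comparison of the two gift-card amounts. Later entrants cannot affect it, since all incentive patients joined in Year 1, and no differential effect of skippers between those groups has been shown.

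Impact is also bounded: repeat comparisons have no power calculation, and the plan calls those between the gift-card amounts exploratory.

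**Conclusion.** The mismatch is real. Under the plan's own invitation rule and repeat range, about 63% to 28% of Year 3 invitees are outside the Year 3 denominator. This rests on the 12% abnormal rate holding in Year 2 and on leaving out patients with an abnormal Year 2 FIT.

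The literal ratio is not a proportion and is inflated by any skipper who returns. The amount cannot be fixed from the documents: at 40% repeat in both years, skipper return of 10% to 40% moves it from 57% to 108%. The nested rate is valid, but it answers a narrower question than completion among those invited in Year 3.

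If Year means program year, first-time completers would inflate the repeat rates of the outreach-alone arm only. The 15 to 17 points above illustrate this for Year 2 and are not an estimate. The problem is confined to the repeat rates in Aims B and C; initial completion and its sample size are untouched.

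**What to change.** Define the Year k repeat rate as patients sent a Year k repeat invitation who complete that kit, divided by patients sent a Year k repeat invitation. State that the numerator is a subset of the denominator and that first-time invitees are excluded. State whether Year counts from program start or from the patient's first invitation. Report Year 3 separately for patients who did and did not complete Year 2, and keep the consecutive-year rate as a separately named outcome.

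The cost is a rewording of two formulas. The initial-rate formula already uses patients sent an invitation as its denominator, and the tracking database is described as recording delivery of all screening interventions and their outcomes. The Year 3 figure will probably look less favourable. The repeat comparison will still condition on a normal Year 1 FIT, which follows randomisation, so it should not be presented as a fully randomised comparison.

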The incentive will consist of either a \$5 or \$10 gift card to a local retailer that will be sent to the patient upon return of an FIT kit. Incentives will be mailed by the JPS outreach team, in exchange for successful FIT completion, after the FIT has been returned. \$5 and \$10 incentives were chosen for several reasons. First, these levels of incentives, if shown effective, could be potentially sustained by the JPS system beyond the timeframe of the grant. Higher incentives, while potentially more powerful in inducing participation, would be unsustainable and therefore do not merit study at this time. Comparing \$5 and \$10 incentives is important because if offering incentives is effective in boosting screening, it is important to know the minimum incentive required for meaningful changes in participation. Incentives are to be offered to all patients who are assigned to the incentive strategy. We considered, but rejected, restricting incentives to only patients who initially do not respond to screening invitations. This was because restricting incentives to non-responders would logistically complicate outreach activities. It is important to note that patients meeting study inclusion criteria must have a minimum of 1 visit to a JPS Primary Care clinic within the last year. Considering these patients have an established baseline relationship with the JPS primary care system, the addition of a modest financial incentive should not create undue influence in patients that otherwise would still have exposure to information on the benefit of screening. Since participation in this standard of care screening poses minimal to no risk, the chances that incentives may motivate research participants to take unnecessary risks are low.

Screening Completion Follow Up. Follow up for determining screening completion for all included patients will be through the end of Year 3 regardless of whether or not patients respond to screening invitations. As is explained below, screening rates will be measured for all patients included for outreach invitations. For patients who die on follow up or who do not have additional health system encounters, follow up will be censored at time of death or last health encounter, respectively.

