The study will evaluate outcomes of large-scale outreach invitation, as well as whether financial incentives have an impact on screening participation in this outreach invitation. All individuals, regardless of the screening group to which they are randomly assigned, will be free to engage in usual medical care, including usual care CRC screening.

b. The waiver would not adversely affect the rights and welfare of the subjects.

The rights and welfare of subjects is not at risk because individuals maintain autonomy, and are being offered standard-of-care CRC screening test with evidence-based benefits. Absence of consent is not anticipated to infringe on the participant's autonomy, as all patients recruited may chose to participate or not participate in screening. Moreover, individuals invited to screening could refuse our invitations and choose to follow up with primary providers to seek screening as part of usual practice.

For patients assigned to receive financial incentives, the level of incentives are likely non coercive. We are studying impact of modest \$5 and \$10 incentives for completing screening. These levels of incentives are unlikely to be coercive. Additionally, for patients in who are not assigned to receive financial incentives in addition to screening promotion, absence of these interventions is unlikely to result in financial hardship. It is important to note that patients meeting study inclusion criteria must have a minimum of 1 visit to a JPS Primary Care clinic within the last year. Considering these patients have an established baseline relationship

with the JPS primary care system, the addition of a modest financial incentive should not create undue influence in patients that otherwise would still have exposure to information on the benefit of screening. Since participation in this standard of care screening poses minimal to no risk, the chances that incentives may motivate research participants to take unnecessary risks are low.

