Evaluation Aim A) Determine screening rate improvement after expanding screening outreach to all unscreened patients. The denominator population for evaluating baseline and end of Year 3 screening rates will consist of patients meeting the following criteria: 1) Age 50-64, 2) Uninsured, but participants in JPS's medical assistance program for the uninsured, 3) One or more visits to a JPS primary care clinic within a year, 4) Address and phone number on file, 5) No history of CRC or colon resection, 6) Not incarcerated

Thus, the denominator population for our baseline and end of Year 3 follow comparisons of screening rates generally includes patients age-eligible for screening outreach. The numerator for calculation of screening rates will be the number of patients who are up-to-date with screening based on colonoscopy within 10 years, sigmoidoscopy within 5 years, or stool blood test (guaiac FOBT or FIT) within the last year, measured by HEDIS criteria. Thus, the screening rate at baseline and at end of Year 3 will be defined by:

Screeni ng Rate ▪ _	# up-to-date with
	screening

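### Aims B and C ask about screening completion but count only FIT, the test the gift card rewards, so the incentive comparison cannot tell added screening from a switch of test

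*Combined protocol and SAP*

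**What the plan says.** **The question.** The Specific Aims and the Biostatistics section pose Aim B as "Compare rates of initial and repeat screening completion among 1) Patients offered a modest financial incentive to complete screening", against patients offered outreach alone. Aim C asks the same of the $5 and $10 groups.

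**The outcome.** Under Evaluation Aim B the initial rate is the number of "patients completing a FIT" in Year 1 over the number "of patients sent FIT invitation Year 1". The test is then stated in FIT terms: "We will compare initial FIT completion rates for the financial incentive plus organized outreach vs. organized outreach alone groups using a Chi-square test". The Year 2 and Year 3 repeat rates also count only FIT, among patients whose FIT in the year before was normal. Evaluation Aim C adopts the same definitions.

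**The incentive.** The Financial incentives section says: "Incentives will be mailed by the JPS outreach team, in exchange for successful FIT completion, after the FIT has been returned".

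**Other screening.** The waiver justification (item a, minimal risk) says that patients in any group "will be free to engage in usual medical care, including usual care CRC screening".

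**The contrast with Aim A.** Its numerator counts patients "up-to-date with screening based on colonoscopy within 10 years, sigmoidoscopy within 5 years, or stool blood test (guaiac FOBT or FIT) within the last year". Aim A compares baseline with the end of Year 3, not the randomized incentive groups.

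**Staying in.** Criteria for Exclusion of Subjects says: "Once included, patients will remain in the program unless they no longer meet age criteria".

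**The concern.** The plan uses two meanings of being screened, and the randomized comparisons get the narrower one. That would matter little if the incentive were neutral between tests, but it is not: a colonoscopy, sigmoidoscopy or guaiac test earns no card and does not enter the Aim B and C numerators.

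Suppose a patient would have had a usual-care colonoscopy under outreach alone. If the card leads that patient to return a FIT, the patient moves from non-completer to completer, while the number of people screened is unchanged. A positive FIT difference could therefore mix new screening with substitution, and the two cannot be separated on the planned outcome. The same applies between $5 and $10 if the larger card causes more switching.

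The repeat rates have a related difficulty. A patient with a normal FIT who then has a colonoscopy or sigmoidoscopy is up to date under the inclusion criteria. The patient nevertheless stays in the denominator and counts as not having repeated.

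At stake is the conclusion the program wants to draw, that incentives promote screening over and above outreach. The Background itself argues that taking part in any test probably matters more than which test is done.

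**Working it through.** **1. The plan's own figures reproduce, and none is in dispute.**
- Aim C: 43% vs 53%, two-sided alpha 0.05, 90% power. n = [1.96·√(2·0.48·0.52) + 1.2816·√(0.43·0.57 + 0.53·0.47)]² / 0.10² gives 523 per group, or 543 with continuity correction. The plan states 545.
- Aim B: 2,000 vs 18,000, 33% vs 38%. Power = Φ[(d − 1.96·SE₀)/SE₁] with d = 0.05, pooled SE₀ = 0.01112 and unpooled SE₁ = 0.01141. The result is 99.3%, consistent with the stated power of over 90%.

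**2. How the FIT difference relates to the screening difference.** Let F₀ and F₁ be the FIT rates in the outreach-alone and incentive groups. Let u be the share who, under outreach alone, have a non-FIT test and no FIT. Let s be the share of those who return a FIT under the incentive. Assume the card does not otherwise change non-FIT testing.
- Any-test rate, outreach alone: F₀ + u
- Any-test rate, incentive: F₁ + u(1 − s)
- Any-test difference: (F₁ − F₀) − s·u

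The FIT difference overstates the screening difference by s·u. If s = 0, u cancels, so equal usual-care colonoscopy in both groups does no harm. For Aim C the overstatement is u times the difference in s between $10 and $5.

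**3. What difference is enough for p<0.05.** The smallest observed difference solves d = 1.96·√[p̄(1 − p̄)(1/n₁ + 1/n₂)].
- Aim B at 33%: p̄ = 0.3322, SE = 0.01110, d = 2.2 points (about 44 of 2,000).
- Aim C at 43%: p̄ = 0.4518, SE = 0.02226, d = 4.4 points (about 44 of 1,000).

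**4. Illustration.** The documents give neither u nor s, so the values below are assumptions. In the Aim C column, s is read as the extra share switching at $10. The last two columns give the chance of p<0.05 in favour of the incentive (or of $10) with no true screening gain, from the formula in step 1. The nominal value is 2.5%.

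| u | s | s·u (points) | Aim B | Aim C |
|---|---|---|---|---|
| 2% | 25% | 0.5 | 7% | 4% |
| 2% | 50% | 1.0 | 15% | 7% |
| 6% | 25% | 1.5 | 27% | 10% |
| 6% | 50% | 3.0 | 77% | 27% |

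Only the last row exceeds the 2.2-point threshold, and none reaches 4.4. The thresholds apply to the observed difference, so smaller shifts raise the false-positive chance without making it likely. An observed 5-point FIT gain would be a 4.5-point to 2.0-point screening gain over the same four rows. At u = 1% the overstatement cannot exceed 1 point.

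**5. Repeat years.** Let v be the share of the denominator with an interval colonoscopy or sigmoidoscopy and no repeat FIT. The FIT repeat rate is coverage minus v in each group. The difference between groups is wrong by the difference in v, and is unaffected if v is equal. No value for v is given.

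**6. Whether another planned analysis covers this.** The logistic models under Secondary analyses reuse the initial completion rate and add a programmatic screening outcome that is not defined. No any-test comparison by incentive group is stated. The data for one are planned: the variable table under Sources of Research Material lists completion, date and result of all CRC screening tests, and follow-up runs to the end of Year 3 for responders and non-responders alike.

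**The case against.** The FIT outcome is deliberate and openly defined. The program mails FIT kits, the card is attached to the FIT, and response to the test offered is a legitimate thing to measure. This stands, and a reader who inferred that the endpoint is invalid or concealed would go beyond the documents.

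A reader might also infer that an outreach-alone patient who has a colonoscopy and counts as unscreened biases the comparison. That does not follow: such patients arise in both randomized groups and cancel unless the card changes their behaviour.

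The strongest objection concerns size. What the documents do say points low. Every patient was overdue despite a primary-care visit within a year. In the prior program, mailed colonoscopy invitations with reminders and navigation reached only 14% in 12 months. Colonoscopy capacity is described as limited. Both groups already hold a free kit with prepaid return, so switching would have to come from $5 or $10 alone. The plan's clinically meaningful difference is 10 points, well above the illustrated range. All of this stands, and it rules out claiming that a false positive is likely. It does not show that switching is zero, and the planned outcome could not reveal it.

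For the repeat rates, the plan gives no power calculation under Aim B and calls the Aim C comparisons exploratory. This lowers the stakes there.

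**Conclusion.** The point holds as a mismatch between the question and the outcome. FIT completion answers whether the card raises FIT completion. It does not by itself answer whether the card raises screening, because a switch from a usual-care test to a rewarded FIT is scored as a gain.

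The bias in the initial comparison is s·u, in favour of the incentive. Its size is unknown and may be well under a point; the 0.5 to 3 points above rest wholly on assumed inputs. The documents do not support saying that switching would produce a significant result in either aim, or that the planned sample sizes are wrong.

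In the repeat years the FIT rate understates coverage in each group. It misstates the difference between groups only if interval testing differs between them, and nothing in the documents shows that it would.

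**What to change.** - Keep FIT completion as the defined outcome for Aims B and C.
- Add a prespecified companion outcome: completion of any HEDIS screening test (the Aim A test types) in the same period, by randomized group and over the same denominators. In the repeat years, count an interval colonoscopy or sigmoidoscopy after a normal FIT as up to date.
- Report the any-test difference with a 95% confidence interval beside the FIT result. Describe the FIT result as FIT completion, and not as increased screening overall, unless the any-test estimate supports that. A formal significance gate is not needed and would bring power questions of its own.
- Define the programmatic screening outcome under Secondary analyses.
- Reconcile the rule on remaining in the program (Criteria for Exclusion of Subjects) with the up-to-date criteria, so that the status of a patient with an interval colonoscopy or sigmoidoscopy is clear.

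The cost is some analysis-plan wording and one more analysis of data already due to be collected. The stated incentive effect may come out smaller if switching occurs; if it does not, the companion result strengthens the claim.
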